- **Aim 3: Expand and refine the BA protocol and manual.** The investigators, rehabilitation clinic staff, and two veterans with TBI will constitute a panel charged with adapting the preliminary manual for TBI for use in the pilot RCT and then monitoring the study on a monthly basis. They will evaluate the BA strategies and assess the interviews for burden and cultural sensitivity. This will lead to a refined BA protocol and manual, to be evaluated in a larger study of BA's efficacy in the future.

Exploratory Aim: We will examine engagement in activity as a possible mechanism that underlies BA effects on depression.

2.2. State the hypotheses to be tested.

This is not applicable in this feasibility study.

3. Resources and Personnel

3.1. Include where and by whom the research will be conducted.

The research will be conducted by the individuals listed in 3.2 at the CMCVAMC.

3.2. Provide a brief description of each individual's role in the study. Be sure to indicate who will have access to protected health information and who will be involved in recruiting subjects; obtaining informed consent; administering survey/interview procedures; and performing data analysis.

[name], RN, FAAN, Principal Investigator

Access to PHI, involved in recruiting, consenting, administering survey/interview procedures at baseline, performing data analysis, providing input into the development of the intervention, participating in the development of presentations and papers arising from the work.

[name], Co-investigator and Project Manager,

Access to PHI, involved in recruiting, consenting, administering survey/interview procedures, and performing data analysis, providing input into the development

of the intervention, participating in the development of presentations and papers arising from the work.

[name], Co-investigator

Chief of the Rehabilitation Medical Service at CMCVAMC

Access to PHI, involved in recruiting, administering survey/interview procedures, assessing the severity of TBI for all veteran study participants, providing input into the development of the intervention, and participating in the development of presentations and papers arising from the work.

[name], OTR/L, Co-investigator

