4.1. Study Design

4.1.1. Describe experimental design of the study. Include sequential and/or parallel phases of the study, including durations, and explain which interventions are standard of care.

This feasibility study assesses feasibility in six domains and provides preliminary evidence of treatment response, through a pilot randomized controlled trial (RCT). The pilot RCT compares the intervention group (BA plus as Treatment as usual) with the control group (Treatment as usual). We will enroll 40 subjects (20 in each

group), conduct a baseline interview, randomize into the two groups, and then conduct a follow-up interview 3 months later. Subsequently, a qualitative phone interview to assess the experience of the intervention along with satisfaction/acceptability will be conducted with those in the intervention group. The BA intervention will be delivered in 6 sessions over 3 months by OTs trained in BA for post-TBI depression.

Procedure. At the baseline interview, the interviewer will review the study, answer veterans' questions, obtain Informed Consent, screen for depression using the CES-D scale and item 9 of the PHQ-9, and conduct the baseline interview battery. If the participant does not meet inclusion criteria based on the CES-D, and PHQ-9 at this time, they will not be included in the study as a randomized participant. We will thank them for their time, and they will receive compensation for the visit. They will also be offered referrals for services as appropriate.

Response cards presenting each question's response format will be employed to reduce response burden and facilitate interview progress. In previous studies, response cards were found helpful and acceptabl.^{47,48} The estimated time of the baseline interview is 1.3 hours, including time for Informed Consent. Interviews of this length have been conducted with veterans with TBI and depression in previous research and were not found excessively burdensome.^{47,48} The interview will be conducted in the setting preferred by the participant, a rehabilitation clinic office or his/her home. In our experience, most who complete the Baseline interview will be willing to continue to participate. Veterans who do not wish to continue with the study after the baseline interview will not be randomized or count towards our accrual goals.

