Within 48 hours of the baseline interview, eligible veterans will be randomized using the method of random permuted blocks (to control for possible changes over time in subject mix) and concealed allocation. Those randomized to BA will be contacted within 5 days by the interventionist and scheduled for the first session.

Those randomized to BA will receive the 6-session BA intervention (as well as treatment as usual [TAU]). Control participants will receive TAU only (which may include current medical and mental health treatments.) Three months after Baseline, a blinded interviewer will conduct the follow-up interview in

person or on the phone with all veterans. Subjects will be sent reminder letters two weeks prior to this 3-month follow-up interview.

Study instruments and when they are used are described in a table in Section 8 and included in the Appendices.

Study staff will offer to share findings with participants.

4.1.2. Include a description of how anticipated risk will be minimized and include an analysis of risk vs. potential benefit.

This study is designed for persons with TBI who have a CES-D score of 16 or greater at both screening and baseline. Such a score indicates the presence of clinically significant depressive symptoms. Those who answer affirmatively (1, 2, or 3) at the baseline interview to item 9 from the PHQ-9, indicating suicide ideation, will not be eligible for the study.

Because this study involves interviews with persons with TBI who have at least mild depression, there is a minimal risk that the interviews may contribute to emotional discomfort in the discussion of personal matters. In our previous study of veterans with TBI in their homes (the large majority of whom scored above the cutoff for clinical depression on the CES-D Short Form), using many of the same interview instruments as proposed, we encountered no upset or excessive fatigue with any participants nor did any adverse events occur as a result of study participation.

The study poses minimal risk to study participants, based on experience with our earlier in-home intervention study with veterans with TBI, the literature on rehabilitation interventions with persons with TBI, and literature on BA. The risk of burden or fatigue from the interview or intervention is also low.

Risks to privacy or subject discomfort about disclosing or considering sensitive information

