Pain and self-rated health	Pain (frequency and intensity) and self-perceived health are especially germane to TBI and depression. These measures are taken from the SF36, ⁷² a well-established measure of health-related quality of life. Baseline interview.
COVID Impact	CAIR Pandemic Impact Questionnaire measures the physical, psychological, and financial impact of the COVID-19 pandemic ⁷³ Baseline and Follow-up interviews
Dose and Intensity	The Delivery Assessment form (Appendix 7) is completed by the OT- interventionist after each session, documenting start and stop times, treatment setting, TBI-related problems worked on, BA components used, and amount of time for each. These data will be used to characterize the intervention content. Each OT-intervention session.
OT-rated Acceptability	This 18-item Acceptability and Enactment Scale is part of the Delivery Assessment Form (Appendix 7) based on measures extensively used by the investigators. ³⁹ Final OT session.
Acceptability and experience of BA to participants	Measures of acceptability and perceived benefits from BA are collected in a final phone interview, immediately after the 3-month follow-up interview, with BA participants Appendix 9). Acceptability by patients – final phone interview.
Acceptability to clinic staff	Questions elicit clinic staff's thoughts about the feasibility and acceptability of a BA-based intervention in the rehabilitation clinic setting. Acceptability by staff – after completion of data collection.

9. **Data Analysis**

9.1. **Provide sample size determination and analysis (include anticipated rate of screen failures, study discontinuations, lost to follow-up etc.).**

This is a feasibility study using 40 subjects. It will assess recruitment, refusal, and retention rates and other indicators of feasibility as described earlier.

9.2. **Describe how, where and by whom the data will be analyzed.**

Data will be analyzed at the CMCVAMC by the PI and Co-Is.

Aim 1 will assess the feasibility of BA in the VA rehabilitation setting, following criteria suggested by Bowen et al.⁵² and Thabane et al.⁵³:

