- (e) Participant comprehension: Interviewer and interventionist will note areas of participant difficulty understanding interview questions and intervention activities. Missing data will also reflect difficulty.
- (f) Research burden: Length of time to complete interviews will be recorded using start and stop time data on the interview. The interviewer will record participant fatigue, wish to take breaks, and/or emotional distress.

Aim 2 will assess change in participant response by comparing Group 1 (BA + TAU) and Group 2 (TAU) on outcomes at T2 (3-month follow-up). We will first conduct

descriptive analyses separately for the BA and control groups to characterize the sample and assess the success of randomization in balancing the two groups. We will inspect trends, directions of change in the two groups, and associations between baseline characteristics (T1) and CES-D scores at follow-up (T2). The same trends and changes will be inspected for the secondary outcomes of CR and QOL. Analyses will be conducted using SPSS version 25.

Aim 3 is to develop and refine the BA protocol, manual, and interview measures. In the first 3 months, an expert panel comprising the investigators, interventionists, interviewer, clinic staff, and two veterans with TBI will review and modify the existing protocol and manual to adapt them for hallmark deficits of TBI. The panel will meet monthly to monitor the study, assessing need for additional compensatory strategies and removal or alteration of strategies that depend on: abstract thinking; patients' understanding of TBI-related depression; awareness of emotion and its regulation; and interpersonal issues. Interview measures will be assessed for participant comprehension, sensitivity, and burden. This pilot study will produce a refined BA protocol and manual for post-TBI depression whose efficacy will be evaluated in a larger RCT.

An Exploratory Aim will examine engagement in activity as the mechanism underlying effects of BA. Although mediation analysis is beyond the scope of this feasibility study, we will explore characteristics of activity engagement using the BADS and its associations with the BA intervention and with depression.

10. Withdrawal of Subjects

10.1. Describe any anticipated circumstances under which subjects will be withdrawn from the research without their consent.

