To maintain the validity and integrity of the data, [name] will be responsible for training the Research Interviewer(s) in enrollment, the ongoing consent process, and data collection procedures and also be responsible for training the OT interventionists in their treatment-documentation procedures. Interviewer training will include a review of the eligibility criteria, study procedures, safety plans, completion and scoring of each of the study instruments, and safeguards to maintain confidentiality. [name] or [name] will observe the several early interviews for each interviewer to assure integrity in the consent process and data collection process and adherence to confidentiality safeguards. They will provide additional training and review as on a regular basis. They will also conduct a weekly inspection of IRB documents, study records, data security, and confidentiality safeguards to ensure that the study is adhering to the study protocol and research regulations. These items will be part of the weekly discussions among the research interviewer, [name], and [name] that will address fidelity to the data collection protocol.

The training for the OT interventionists will include a review of the study protocol, confidentiality safeguards, and the safety plan for study participants who may need additional medical or mental health services. The interventionists will meet with the [name] twice monthly for debriefings. The co-investigator, [name], will also observe at least five randomly selected intervention visits in Months 1-2 to monitor fidelity to the study protocol and confidentiality safeguards.

Treatment Fidelity Monitoring

We will monitor delivery of the intervention using a plan for providing oversight of treatment implementation based on the NIH Behavioral Change Consortium's recommendations for assessing and maintaining treatment fidelity.^{76,77} The plan involves standardizing delivery and checking for protocol adherence utilizing three general strategies: following a treatment manual, checking adherence to the protocol, and maintaining provider skills. Specific steps to achieve treatment fidelity goals include the following:

- (a) *The Behavioral Activation condition is manualized to insure standardization of delivery.*

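### The 3-month interviewer is promised to be blinded, yet the interviewer sits with the interventionists on the monthly panel that reviews and alters the BA strategies

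*Combined protocol and SAP*

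**What the plan says.** **The blind.** Section 4.1.1 (Procedure): "Three months after Baseline, a blinded interviewer will conduct the follow-up interview in" person or by telephone, for all veterans.

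**The panel.** Section 9.2 (Aim 3) describes "an expert panel comprising the investigators, interventionists, interviewer, clinic staff, and two veterans with TBI". In the first 3 months it adapts the manual. After that: "The panel will meet monthly to monitor the study, assessing need for additional compensatory strategies and removal or alteration of strategies". Section 2.1 (Aim 3) gives a shorter membership: "The investigators, rehabilitation clinic staff, and two veterans with TBI will constitute a panel charged with adapting the preliminary manual for TBI". It also says that the panel monitors the study monthly after the manual is adapted. It names neither the interviewer nor the interventionists.

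**Treatment timing.** Section 4.1.1: "The BA intervention will be delivered in 6 sessions over 3 months by OTs trained in BA for post-TBI depression". Treatment therefore fills the interval between baseline and follow-up.

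**Other contact points.**
- Section 9.2, Aim 1(e): "Interviewer and interventionist will note areas of participant difficulty understanding interview questions and intervention activities".
- Data and Safety Monitoring Plan, on checks of study records and confidentiality: "These items will be part of the weekly discussions among the research interviewer" and two senior team members. The same plan also refers to interviewers in a form that allows for more than one.
- Table 2 places the BA-only acceptability call "immediately after the 3-month follow-up interview, with BA participants". It does not say who makes the call.

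**The concern.** The panel's monthly task is to judge which BA strategies are not working for people with TBI. That judgement would naturally draw on how treated veterans are getting on, and the interventionists who treat them are in the room. An interviewer who hears this, and who has met the veterans at baseline, may work out who is in the BA arm before scoring them at 3 months.

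The blinded interviewer is the only blinding measure promised for the Aim 2 outcomes: CES-D, community reintegration and quality of life. All three are collected by interview, compared descriptively and meant to inform a larger trial. Veterans know their own arm, so bias in their own reporting stays whatever is done. What is at stake is the interviewer's share of the bias, and whether a later report can fairly say that outcome assessment was blinded.

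**Working it through.** The plan gives no figure to reproduce here. The check compares the provisions and then works out the exposure from the stated schedule.

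**1. Do panel meetings overlap with follow-up?** Yes. Sections 2.1 and 9.2 both have the panel adapt the manual first and then monitor the study monthly, so meetings continue while veterans are treated and followed.

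**2. Is the interviewer present?** Under section 9.2, yes. The sentence on monthly meetings refers back to the panel just listed. Under section 2.1 the interviewer is not named, but the investigators still are. In section 3.2 the principal investigator's interviewing is limited to baseline. The co-investigator who is project manager and the co-investigator who heads the rehabilitation service also administer interviews, with no such limit. The Treatment Fidelity Monitoring section has the investigators attend twice-monthly case conferences with both interventionists. Under either list, someone allowed to do a 3-month interview may sit where BA delivery is discussed.

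**3. Is there a safeguard?** None was found.
- Concealed allocation (4.1.1) protects the assignment, not later assessment.
- Code numbers, password protection and restricted tracking files (4.1.2 and 12.2) protect confidentiality.
- Interviewer training (6.3 and the Data and Safety Monitoring Plan) covers consent, eligibility, scoring, safety and confidentiality, but not keeping the blind.
- The available text does not say that panel cases are anonymised, that the interviewer leaves for BA items, or that unblinding is recorded.

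**4. How much exposure?**
- Inputs: baseline to follow-up 3 months (4.1.1); panel monthly (9.2); 20 veterans in the BA arm, each treated over 3 months (4.1.1). The length of accrual is not given, so 12 to 24 months at a steady rate is assumed.
- Panel meetings per veteran between baseline and follow-up: 3 months × 1 per month = about 3.
- BA veterans in treatment at one time = 20 × 3 / accrual months:

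| Assumed accrual | Calculation | BA veterans in treatment at once |
|---|---|---|
| 12 months | 20 × 3 / 12 | 5.0 |
| 18 months | 20 × 3 / 18 | 3.3 |
| 24 months | 20 × 3 / 24 | 2.5 |

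With so few in treatment, leaving out a name may not hide who is being described.

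**5. Does the acceptability call add to the risk?** Only conditionally. It comes after the 3-month data are recorded and cannot change them. It matters only if the follow-up interviewer is told the arm beforehand in order to make the call.

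**The case against.** The strongest reply is that the panel's stated business is content, not cases. Its remit is which strategies lean on abstract thinking, emotional awareness or interpersonal skills, together with a review of the interview measures. Knowing the BA manual does not reveal any veteran's arm. Discussion of individual veterans appears to belong to the case conferences and the interventionists' debriefings, and neither names the interviewer. The line on noting comprehension difficulties can be read as each person noting problems in their own task. There may be several interviewers, so the one on the panel need not be the one at follow-up. Part of the staff-role list in section 3.2 and the interview batteries were not available, and either could contain a safeguard. Finally, no hypothesis is tested, Aim 2 is descriptive, the Aim 1 criteria do not depend on this blind, and fixed response formats limit an interviewer's influence.

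Much of this stands. It shows that unblinding is a possibility and not a certainty, and that the comprehension line is weak support on its own. It does not supply the missing separation. No available text keeps the follow-up interviewer away from discussion of BA delivery, and the shorter panel list does not cure this, for the reason in step 2 of the working. That Aim 2 is descriptive lowers the stakes, but its results are still intended as preliminary data for a larger trial.

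**Conclusion.** The concern holds as a risk to the blind. The plan promises a blinded follow-up interviewer, seats the interviewer monthly with those who deliver BA, and states no arrangement to keep the two compatible. The exposure is about 3 meetings per veteran, with roughly 2.5 to 5.0 BA veterans in treatment at a time if accrual takes 24 to 12 months. No size of bias in CES-D or the secondary outcomes is claimed, because the documents give no basis for one.

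The conclusion assumes that panel meetings touch on how treated veterans are doing, and that the panel's interviewer, or an investigator who interviews, may also conduct 3-month interviews. Neither is stated and neither is excluded. Confidence is medium. This is a change that should be made, not a flaw that undermines the feasibility aims.

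**What to change.** - State who conducts the 3-month interviews. Keep that person, including any investigator in that role, out of panel sessions and case conferences that discuss BA delivery until the last 3-month interview is done.
- Let that person take part in the manual adaptation before the pilot RCT, and afterwards give comprehension and burden feedback in writing without participant identifiers.
- State that the interviewer is not told a veteran's arm before that veteran's 3-month data are recorded, and that an existing unblinded team member makes the BA-only acceptability call.
- Add an item at the end of the 3-month form recording whether the arm was learned.
- Reconcile the panel membership in sections 2.1 and 9.2.

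The cost is protocol wording, one form item and use of existing staff. The drawback is that, once veterans are in treatment, the panel has the interviewer's input in writing instead of in person. If the roles are already separated in practice, a sentence saying so and the aligned panel lists would settle most of the point.
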